8.9 Study Termination

The study may be stopped at his/her study site at any time by the site investigator. Allergan may stop the study (and/or the study site) for any reason with appropriate notification.

9. Adverse Events

Adverse events occurring during the study will be recorded on an adverse event eCRF. If adverse events occur, the first concern will be the safety of the study participants.

9.1 Definitions

9.1.1 Adverse Event

An adverse event is any untoward medical occurrence in a patient or clinical investigation patient administered a pharmaceutical product and that does not necessarily have a causal relationship with this treatment. An adverse event can therefore be any unfavorable and unintended sign (including an abnormal laboratory finding), symptom, or disease temporally associated with the use of a medicinal (investigational) product, whether or not related to the medicinal (investigational) product. In addition, during the screening period, adverse events will be assessed regardless of the administration of a pharmaceutical product.

Note: Adverse events must be collected once informed consent has been obtained, regardless of whether or not the patient has been administered study drug.

Progression of OAB, including new or worsening of anticipated clinical signs or symptoms, which are collected as clinical efficacy variables and assessed as unequivocally associated with the disease progression and /or lack of efficacy, should not be reported as adverse events unless the disease progression is greater than anticipated in the natural course of the disease.

Adverse events will be assessed, documented, and recorded in the eCRF throughout the study (ie, after informed consent has been obtained). At each visit, the investigator will begin by querying for adverse events by asking each patient a general, non-directed question such as “How have you been feeling since the last visit?” Directed questioning and examination will then be done as appropriate. All reported adverse events will be documented on the appropriate eCRF.

9.1.2 Study-specific Definitions for Particular Adverse Events

Definition of Adverse Event of Urinary Retention:

An adverse event of urinary retention should only be recorded when a patient has a raised PVR that requires intervention with CIC according to the following criteria:

- patient has a PVR of ≥ 350 mL (regardless of symptoms), OR
- patient has a PVR ≥ 200 mL and < 350 mL and the patient reports associated symptoms ie, sensation of bladder fullness or inability to void despite persistent effort, that in the investigator's opinion require CIC.

Definition of Adverse Event of Residual Urine Volume:

An adverse event of residual urine volume should be recorded if, in the investigator's opinion, the raised PVR is clinically significant but does not fulfill the above definition for urinary retention.

Definition of Adverse Event of Urinary Tract Infection

An adverse event of UTI will be recorded if both the following criteria are fulfilled, regardless of patient symptoms:

- a positive urine culture result with a bacteriuria count of $> 10^5$ CFU/mL
- leukocyturia of > 5 /hpf

If a patient meets the criteria for the definition of a UTI, the investigator will record whether the UTI was "symptomatic" or "asymptomatic" on the adverse event eCRF

Note: If urinalysis/culture results are reported which, in the opinion of the investigator, are considered clinically significant but do not fulfill the above definition of a UTI, the findings should be recorded as adverse events (eg, bacteriuria, leukocyturia).

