6.3.9 Post-void Residual (PVR) Urine Volume

PVR urine volume is assessed at screening and at every posttreatment clinic visit by ultrasound or bladder scan after the patient has performed a voluntary void. PVR urine volume can be assessed at any other time depending on clinical need. PVR measurements will not be done by catheterization.

Should a PVR urine volume indicate a clinically meaningful elevation (as defined below), the patient should be asked to void once again (allowing the patient sufficient time to void). The

PVR urine volume will then be re-assessed. For patients who have a PVR urine volume measurement repeated, only the repeat value should be recorded in the eCRF.

Guidance on how to manage an elevated PVR, observed at any routine study visit or unscheduled visit is provided. In summary, posttreatment PVR urine volume is divided into 3 categories:

- i) < 200 mL
- ii) between ≥ 200 mL and < 350 mL
- iii) ≥ 350 mL

Protocol required action depends on the PVR category as does the need for further visits to evaluate the patient. Protocol-required need for CIC is also dependent on the PVR as well as the patient symptoms. This guidance is to ensure patients are appropriately followed up and CIC is only initiated when required (while also ensuring any unnecessary intervention is limited). Further details are given below.

This guidance does not preclude further actions if the investigator deems it necessary.

i) PVR < 200 mL

No protocol required action needs to be taken. Patient continues to be reviewed as per the schedule of visits and procedures.

ii) PVR ≥ 200 mL and < 350 mL

If a PVR of ≥ 200 mL but < 350 mL is identified at any posttreatment visit, the investigator will assess the patient for any spontaneously reported associated symptoms (such as voiding difficulties or sensation of bladder fullness), with the resulting action to be as follows:

- a) If a patient reports associated symptoms that in the opinion of the investigator requires CIC to be initiated, then CIC should be managed as detailed in the CIC section.
- b) If a patient does not report any symptoms or if they report associated symptoms that, in the opinion of the investigator, do not require CIC then the following will occur:

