- The patient will be seen for an additional follow-up visit 1 week later, at which time the PVR and any associated symptoms will be reassessed and a urine dipstick, central laboratory urine analysis, and culture/sensitivity will be performed. At this reassessment visit:
 - If the PVR is increasing and is associated with symptoms, that in the investigator's opinion require CIC, then CIC should be initiated and managed as detailed below in the CIC section
 - If the PVR is ≥ 350 mL then CIC should be initiated and managed as detailed below in the CIC section
 - If the PVR is increasing but is not associated with symptoms or is associated with symptoms that in the opinion of the investigator do not require CIC, then the patient will be seen 1 week later to determine if CIC has become warranted and should be initiated based on PVR and/or any associated symptoms. At this additional reassessment visit:
 - A urine dipstick, central laboratory urine analysis and culture/sensitivity will be collected
 - If in the investigator's judgment CIC should be initiated, then CIC should be managed as detailed below in the CIC section
 - If CIC is not initiated and PVR continues to increase, the investigator will determine whether the patient will be followed at regularly scheduled study visits or whether additional follow-up visits should occur
 - If the PVR is decreasing or is unchanged then the patient will continue to be reviewed as per the schedule of visits and procedures.

iii) PVR ≥ 350 mL

If a PVR of ≥ 350 mL is identified at any posttreatment visit (regardless of symptoms) then CIC will be initiated as detailed in the CIC section.

Clean Intermittent Catheterization

The following guidance should be used for the initiation and cessation of CIC in this study. Sterile, single-use intermittent catheters should be used. Indwelling catheters should not be used in this study, therefore the Allergan Medical Safety Physician should be informed if an indwelling catheter is utilized.

Initiation of Clean Intermittent Catheterization

As described above in the PVR section, CIC should be initiated when one of the following criteria is fulfilled:

- PVR is ≥ 350 mL at any posttreatment visit, regardless of whether the patient reports associated symptoms
- PVR is ≥ 200 mL and < 350 mL and the patient spontaneously reports associated symptoms (ie, voiding difficulties, sensation of bladder fullness) that in the opinion of the investigator requires CIC

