6.3.13.1 Adverse Events of Urinary Tract Infection

Please refer to Section 9.1.2 for the study-specific definition of UTI adverse events. If a patient meets the criteria for the definition of a UTI, the investigator will record whether the UTI was “symptomatic” or “asymptomatic” on the adverse event eCRF.

If a patient reports a UTI to the investigator that was evaluated by a physician not at the investigative site (eg, primary care physician or emergency room), then all reasonable attempts will be made to obtain the confirmatory urine analysis and culture/sensitivity results. In such instances, the UTI should still be captured on the adverse event eCRF.

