### **4.4 Concomitant Medications/Procedures**

Concomitant medications are defined as those taken on or after the first study treatment, regardless of when the medications started. The number and percentage of patients taking each medication will be presented by WHO DDE preferred drug name for all BOTOX group.

All prophylactic antibiotic medication associated with study drug treatment will be summarized by WHO Drug Class and WHO DDE preferred drug name.

Concurrent procedures are defined as those undertaken on or after the first study treatment. A list of concurrent procedures will be provided for all BOTOX group.

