### **6.6.4 Use of Clean Intermittent Catheterization Post-treatment**

A listing of patients will be produced for patients using CIC containing all data from the eCRF information page.

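### Read literally, the urinary retention definition cannot record acute retention that is drained without a PVR scan, so such an event would fall under another term and leave the by-dose retention count.

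*Protocol*

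**What the plan says.** Protocol 9.1.2 restricts the term: "An adverse event of urinary retention should only be recorded when a patient has a raised PVR that requires intervention with CIC". It then gives two criteria. The first reads "patient has a PVR of ≥ 350 mL (regardless of symptoms), OR". The second covers a PVR from 200 mL to below 350 mL with "sensation of bladder fullness or inability to void despite persistent effort, that in the investigator's opinion require CIC". The section's fallback term, residual urine volume, is for a raised PVR that matters clinically but falls short of retention.

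Protocol 6.3.9 measures PVR by ultrasound or bladder scan once the patient has voided voluntarily, and adds "PVR measurements will not be done by catheterization". Extra scans are allowed whenever there is a clinical need. When CIC is started, a retention event is to be recorded. Indwelling catheters are not meant to be used, and the sponsor's safety physician "should be informed if an indwelling catheter is utilized". No adverse event term is given for that case.

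For urinary tract infection, Protocol 6.3.13.1 deals with evaluation by a physician outside the site: "In such instances, the UTI should still be captured on the adverse event eCRF". Retention has no such clause.

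On outputs, SAP 6.2 tabulates coded adverse event terms by treatment group and cycle. SAP 6.6.3 tabulates PVR categories. SAP 6.6.4 says "A listing of patients will be produced for patients using CIC", and SAP 4.4 says "A list of concurrent procedures will be provided for all BOTOX group".

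**The concern.** The definition depends on a measurement that may not exist in the most acute form of the event. A patient who cannot void between visits and is drained in an emergency department may have no scan and may never start CIC. The restrictive wording of 9.1.2 then directs the site away from the retention term.

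Protocol section 1 names retention among the dose-dependent harms seen in the adult phase 2 study, and Protocol section 7 says the primary analysis was to support the paediatric dose recommendation. SAP section 1 now plans a single analysis, but retention by dose remains a central safety result. Counts per arm will be small, so the classification of a single event is visible in the table.

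**Working it through.** The plan states no figure on this point, so there is none to reproduce. The check has two parts.

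**Tracing an unscanned event through the rules.** Take a patient who cannot void, is drained by catheter without a scan, and recovers before the next visit.

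1. Retention, first criterion (9.1.2): needs a PVR of 350 mL or more. There is no scan, and 6.3.9 does not accept the drained volume. Not met.
2. Retention, second criterion (9.1.2): needs a PVR from 200 mL to below 350 mL. Not met, although inability to void is one of its listed symptoms.
3. Residual urine volume (9.1.2): also presupposes a raised PVR. Not met.
4. The retention entry tied to starting CIC (6.3.9): CIC was not started. Not triggered.
5. Outside-care clause: exists for urinary tract infection (6.3.13.1), not for retention.
6. General rule (9.1.1): every reported adverse event goes on the eCRF. The event is recorded, but under some other term.
7. SAP outputs: the event is in the adverse event tables (6.2) under that other term. It is not in the PVR categories (6.6.3), because no value was taken, nor in the CIC listing (6.6.4). It may be in the concurrent-procedures list (4.4), which is specified for the all-BOTOX group and not by dose.

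Now change one fact: a scan shows 350 mL or more and an indwelling or one-off catheter is then used. Step 1 is met, because the criterion turns on the volume and the need for CIC, not on the device. The gap is the missing scan, together with silence on the term to use when the catheter is not CIC.

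**Scale (illustration only).** Inputs: 32 patients per arm, or 36 with the 10% allowance (108 / 3), from Protocol 4.1; 6.5% of adults starting CIC after 100 U, from Protocol section 1. Applying that adult CIC rate to retention in an adolescent arm is an assumption.

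- Expected events: 32 × 0.065 = 2.08; 36 × 0.065 = 2.34.
- Weight of one event: 1/32 = 3.1 percentage points; 1/36 = 2.8 percentage points.
- Two events in 32 give 6.25% (exact 95% CI 0.8% to 20.8%). If one is miscoded, the table shows 1/32 = 3.1% (0.1% to 16.2%).

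Let m be the share of events miscoded, which the documents do not give. The recorded rate is 6.5% × (1 − m), and the chance that an arm of n shows no retention event is (1 − 0.065 × (1 − m))^n.

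| m (assumed) | Recorded rate | No event, n = 32 | No event, n = 36 |
|---|---|---|---|
| 0 | 6.5% | 12% | 9% |
| 10% | 5.9% | 15% | 11% |
| 25% | 4.9% | 20% | 17% |
| 50% | 3.3% | 35% | 30% |

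If m is the same at every dose, the recorded difference between two doses is (1 − m) times the true difference, and the ratio is unchanged.

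**The case against.** The other side has a good deal to say. CIC is the planned route: every patient must be willing and able to use it (Protocol 4.3), and catheters are supplied. Scans may be done at any time, sites have ultrasound, and patients stay under observation on treatment day until they void (5.9.4). The second criterion lists inability to void, so its authors foresaw a PVR in such a patient, and nothing in 9.1.2 bars a scan done elsewhere. Patients are told to call about difficulties and report hospitalisations (8.4), the diary records catheterisation (6.3.5), and the SAP has no step that removes a retention entry failing the definition. A site may therefore enter the term anyway.

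These points make the gap smaller but do not close it. They help only if a scan is done or if the site departs from the stated rule.

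Three stronger readings are tempting, and the documents do not support them:

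- That relief by an indwelling or one-off catheter excludes the event. A qualifying scanned PVR meets the definition whatever the device.
- That such events vanish from all outputs. A scanned episode enters the PVR categories whatever term is used, and an unscanned one is still tabulated by dose under its own term.
- That the retention rate is shown to be too low and the dose contrast pulled towards zero. The missed share is unknown and could be zero. An equal share at each dose would shrink the difference but leave the ratio unchanged.

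**Conclusion.** The gap is real but narrow. Following the protocol as written, retention drained without a PVR scan has no route to the retention term or to residual urine volume, and the term for a non-CIC catheter is left open. The consequence is possible miscoding and loss from the by-dose retention count, not loss of the event.

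Its frequency and its effect on the dose contrast cannot be derived from the documents. The figure of about 3 percentage points per event assumes the planned arm sizes, and the expected 2 events per arm also assumes that the adult CIC rate carries over. The SAP's amendment table says recruitment was stopped. If the arms are smaller than planned, each event weighs more.

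**What to change.** Change recording and analysis only; patient care is untouched.

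- **Protocol 9.1.2:** add that urinary retention is also recorded when a patient is catheterised by any method, at the site or elsewhere, because of inability to void or to empty the bladder, even if no PVR scan was done.
- **Outside care:** add a capture clause for retention modelled on the one for urinary tract infection in 6.3.13.1, and record catheter type, place and date on the eCRF.
- **SAP 6.2 and 6.6.4:** tabulate these events, and all post-treatment catheterisations, by cycle and actual dose. Flag events that meet the CIC-only definition and events on the day of treatment.

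If conduct is too far advanced to amend the protocol, the sponsor can review adverse event terms, concurrent procedures and notifications to the safety physician before the single database lock, and add the tabulation.

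The cost is a sentence and a clause in the protocol, a few eCRF fields and some table rows. The retention rate may come out slightly higher, and it may take in events due to the procedure or the anaesthesia. The flags separate those events and preserve the CIC-only rate for comparison.

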9.1.3 Serious Adverse Event

A serious adverse event is any adverse event occurring at any dose that results in any of the following outcomes: death, a life-threatening adverse event, inpatient hospitalization or prolongation of existing hospitalization, a persistent or significant disability/incapacity, or a congenital anomaly/birth defect. Important medical events that may not result in death, be life-threatening, or require hospitalization may be considered a serious adverse event when, based upon appropriate medical judgment, they may jeopardize the patient or patient and

may require medical or surgical intervention to prevent one of the outcomes listed in this definition. (See Section 9.3 for procedures for reporting a serious adverse event.)

Allergan considers all cancer adverse events as serious adverse events. In addition, Allergan considers any abortion (spontaneous or nonspontaneous) as a serious adverse event.

Pre-planned surgeries or procedures for pre-existing, known medical conditions for which a patient requires hospitalization is not reportable as a serious adverse event.

Any pre-planned surgery or procedure should be clearly documented in the site source documents by the medically qualified investigator at the time of the patient's entry into the study. If it has not been documented at the time of the patient's entry into the study, then it should be documented as a serious adverse event and reported to Allergan.

9.1.4 Severity

A clinical determination will be made of the intensity of an adverse event. The severity assessment for a clinical adverse event must be completed using the following definitions as guidelines:

Mild	Awareness of sign or symptom, but easily tolerated.
Moderate	Discomfort enough to cause interference with usual activity.
Severe	Incapacitating with inability to work or do usual activity.
Not applicable	In some cases, an adverse event may be an "all or nothing" finding which cannot be graded.

9.1.5 Relationship to Study Drug or Study Procedure

A determination will be made of the relationship (if any) between an adverse event and the study drug or study procedure, as applicable. A causal relationship is present if a determination is made that there is a reasonable possibility that the adverse event may have been caused by the drug or study procedure.

9.2 Procedures for Reporting Adverse Events

Any adverse event must be recorded on the appropriate eCRF.

All adverse events that are drug-related and unexpected (not listed as treatment-related in the current Investigator's Brochure) must be reported to the governing IRB/IEC as required by

the IRB/IEC, local regulations, and the governing health authorities. Any adverse event that is marked “ongoing” at the exit visit must be followed-up as appropriate.

9.3 Procedures for Reporting a Serious Adverse Event

Any serious adverse event occurring during the study period (beginning with informed consent/assent) and for at least 12 weeks after the last dose of study drug must be immediately reported but no later than 24 hours after learning of a serious adverse event. Serious adverse events must be reported to Allergan (or Agent of Allergan) as listed on the Allergan Study Contacts Sheet and recorded on the serious adverse event form. All patients with a serious adverse event must be followed up and the outcomes reported. The investigator must supply the sponsor and the IRB/IEC with any additional requested information (eg, autopsy reports and discharge summaries).

In the event of a serious adverse event, the investigator must:

1. Notify Allergan immediately by fax or email using the serious adverse event form (contact details can be found on page 1 of the serious adverse event form phone numbers and relevant Allergan personnel contacts are also on the front page of protocol.
2. Obtain and maintain in his/her files all pertinent medical records, information, and medical judgments from colleagues who assisted in the treatment and follow-up of the patient.
3. Provide Allergan with a complete, written description of the adverse event(s) on the serious adverse event form describing the event chronologically, including any treatment given (eg, medications administered, procedures performed) for the adverse event(s). Summarize relevant clinical information about the event: signs, symptoms, diagnosis, clinical course and relevant clinical laboratory tests, etc. Include any additional or alternative explanation(s) for the causality which includes a statement as to whether the event was or was not related to the use of the investigational drug.
4. Promptly inform the governing IRB/IEC of the serious adverse event as required by the IRB/IEC, local regulations, and the governing health authorities.

9.4 Procedures for Unmasking of Study Medication

When necessary for the safety and proper treatment of the patient, the investigator can unmask the patient’s treatment assignment to determine which dosage of BOTOX has been

assigned and institute appropriate follow-up care. When possible, the sponsor (Allergan Medical Safety Physician) should be notified prior to unmasking study medication. The investigator should inform the sponsor (Allergan Medical Safety Physician) of the unmasking if there is no notification prior to the unmasking.

The treatment assignment for the patient can be determined by designated site personnel calling into the IVRS or IWRS system via password protected access. The reason for breaking the code must be recorded in the patient's source documents.

10. Administrative Items

This protocol is to be conducted in accordance with the applicable Good Clinical Practice (GCP) regulations and guidelines, eg, the International Conference on Harmonisation (ICH) Guideline on GCP.

